#### 4.3.6. Questionnaire

A household-based questionnaire will be administered to one member of each participating household to adjust for known influencing factors with regard to reinfection and infection intensity [33, 34] in the subsequent analysis and to identify risk factors for residual infections [35]. The questionnaire will include assessment of / questions about information on socioeconomic characteristics (e.g structure, condition and amenities), access to sanitation and water facilities (e.g. latrine, toilet, shower, water source) as well as hygiene behavior (e.g. defecation, hand washing, water use). The questionnaire is based on the core questions recommended by WHO and UNICEF. To assess environmental risk factors, soil and water samples will be taken at specific sites in the village and analyzed microscopically.

#### 4.4. Measure to minimize bias

Study participants eligible for treatment will be randomly assigned to one of the seven treatment arms (trial A: DF study) or to one of the two treatment arms (trial B: parallel group study) using a computer-generated stratified by 3 levels of baseline infection intensity (light  $\geq$ 0.4 (trial A) or 0.1 (trial B) – 1 LPG, moderate >1-10 LPG and heavy >10 LPG), block randomization code. The random allocation sequence with varying random blocks of 7 or 14 (trial A) and 2 or 4 (trial B) will be provided by a statistician not involved in enrolment, treatment, and data collection. Stratification will guarantee similar proportion of participants with different infection intensities in all treatment arms. The number of light vs moderate vs. heavy infections, however, are not expected to be equal in each arm, depending on the distribution of infection intensity in the recruited cohort. The codes will be held in a locked cabinet at the Swiss Tropical and Public Health Institute. A copy of this code will be kept in a sealed envelope by one of the co-investigators (will only be opened in emergency situations, determined by the principal investigator upon consultation with the co-investigators). The blinding will be maintained throughout the trial until data entry and processing are complete and the data have been verified. Following release of the final data, the randomization codes will be released.

In previous studies [36] we have observed moderate cure and larvae reduction rates in placebo treated children which are in most cases likely due to the imperfect sensitivity of anthelminthic diagnostics. Participants treated with placebo will be treated at follow up (4 post treatment) with ivermectin (200  $\mu$ g/kg). This treatment delay does not cause noteworthy harm.

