## 4.2. Type of trial

Single blinded, randomized placebo-controlled, dose-ranging trial (trial A: DF study) (participants and lab technicians are blinded).

[figure not shown]
Double blinded, randomized, non-inferiority trial (trial B: parallel group study).

The PK sub-studies of trial A and trial B are single blinded.

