#### 5.4. Treatment of subjects

2 mg tablets of moxidectin will be obtained from Medicines Development for Global Health (MDGH), Australia. Ivermectin (3 mg) will be purchased from Merck, Switzerland. Matching placebo tablets (moxidectin and ivermectin) will be obtained from the Medicines Development for Global Health (moxidectin) and produced and a certificate of manufacture and analysis provided by the University of Basel (ivermectin). The appropriate doses will be calculated and the correct amount of moxidectin and placebo (trial A) and moxidectin, moxidecin placebo or ivermectin or ivermectin placebo tablets (trial B) will be administered to all participants. Due to blinding the tablets will be repacked into neutral separate opaque plastic bags each containing the adequate dose of moxidectin tablets and/or placebo tablets (trial A). In trial B, the tablets will be handed out from the drug container according to the randomization list. Each person will receive (i) either 4 moxidectin or 4 moxidecin placebo tablets and (ii) the number of ivermectin tablets with regard to their weight category or the corresponding number of ivermectin placebo tablets. The tablets will as long as applicable be stored in the original package and at any time (except treatment day) be stored according to manufacture prescription, sealed and away from light.

The principal investigator(s) or co-investigator(s) is responsible for drug accountability at the study site. Maintaining drug accountability includes careful and systematic study drug storage, handling, dispensing and documentation of administration.

Treatment and blood sampling (capillary blood sampling for a total of 90 participants, in trial A and venous blood sampling for 10 patients (trial A)) will be done community-based in local temples, that are quiet and spacious locations, where people like to gather and organize meetings. Infrastructure as required for the study needs (i.e tables, chairs, a fridge, a cover from rain and sun) will be installed as necessary at the specific study days. Opportunities

(approximately three daybeds) will be provided to comfortably withdraw the venous blood (4 samples on day 1 and 4 samples within the next 28 days) and to provide a possibility to lie down in case of an arising unwell feeling. Participants will receive a breakfast two hours prior to treatment as well as lunch during the day once absorption of the drug is complete.

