On each treatment day a subgroup of participants will be treated with the different dosages. All drugs will be administered in the presence of the investigator(s) or co-investigator(s) and the physician, and ingestion confirmed. This will be recorded with the time and date of closing. Subjects will be asked not to take any drugs other than those prescribed by the study medical team. After ingestion of the medication, the subjects will be observed for 3 hours to ensure retention of the drug. Vomiting within 1-hour post-dosing will require re-dosing. The subjects will not be allowed more than one repeated dose. No re-administration will be needed for subjects vomiting after one hour. In case any SAE will be observed, the study will be put on hold until the data has been reviewed and a decision taken within the entire study team whether the study can be continued or has to be stopped. On the treatment day, participants presenting a serious medical situation as judged by the physician of the project will be kept at the hospital level under close supervision by the medical team. Also, in order not to break the surveillance of the undesirable effects of those whom we will allow to go back home at the end of the treatment day, security measures will be taken: (i) a card containing at least three phone numbers of the investigators and the study physician will be given to the participant himself. We will be working with adults in rural areas. Participants who are involved in agricultural activities and migrating between locations will be provided with phone numbers so to follow them up with the help of health workers in case AEs occur.

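### Trial B's only described emergency unblinding route is one sealed copy of the whole randomisation code, so a single opening shows every participant's assignment instead of one

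*Combined protocol and SAP*

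**What the plan says.** Section 4.2 describes trial B as "Double blinded, randomized, non-inferiority trial (trial B: parallel group study". Section 4.4 has the allocation sequence prepared by a statistician with no part in recruitment, dosing or data collection, and the codes locked away at the sponsor's institute. It then provides for emergencies: "A copy of this code will be kept in a sealed envelope by one of the co-investigators (will only be opened in emergency situations", the emergency being "determined by the principal investigator upon consultation with the co-investigators". The same section commits that "The blinding will be maintained throughout the trial until data entry and processing are complete and the data have been verified".

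On dispensing, section 5.4 says: "In trial B, the tablets will be handed out from the drug container according to the randomization list". The scheme is double-dummy: "Each person will receive (i) either 4 moxidectin or 4 moxidecin placebo tablets", plus active or placebo ivermectin tablets in a number set by weight. Section 5.4 makes an investigator or co-investigator at the site responsible for accountability: "Maintaining drug accountability includes careful and systematic study drug storage, handling, dispensing and documentation of administration". Neither section says whether the list used for dispensing is masked, or who holds it.

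**The concern.** An emergency break should disclose one participant's treatment and leave the rest of the trial blinded. Section 4.4 describes one envelope holding a copy of the code. To be of use in an emergency that copy must identify the drug, so whoever reads it learns far more than the emergency requires. A proper use of the plan's own provision would end the blind for that reader long before the point to which 4.4 commits.

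Two things could then be affected. If recruitment is still open, the reader knows assignments not yet used, which weakens allocation concealment and could bear on the primary cure-rate comparison. If the reader also assesses adverse events, the remaining gradings and Day 28 interviews are no longer blinded.

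**Working it through.** **1. How many assignments the code covers.** Inputs from section 7.2: true cure rate 89% in both arms, margin 10 points, 80% power, two-sided 95% interval (one-sided 0.025), 10% loss to follow-up.

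n per arm = (1.960 + 0.842)² × 2 × 0.89 × 0.11 / 0.10² = 7.849 × 0.1958 / 0.01 = 153.7, so 154. This matches the plan. Allowing for dropout, 154 / 0.9 = 171.1, so 172 per arm and 344 in total. The planned 350 reads as rounding up. The sample size is not in question; 350 is the number of assignments at stake.

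**2. What one opening shows.** With one copy of the whole code: 350 of 350. With a participant-level break: 1 of 350 = 0.29%. Section 4.4 stratifies by infection intensity only and mentions no separate code per country. If the code were nevertheless split by country, one opening would show that country's share. The documents do not give the split, but either share is far more than one participant.

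**3. Whether another route exists.** Treatment (5.4), safety (6.1 to 6.4) and data management (section 10) describe no individual envelopes, numbered kits or key holder who discloses one participant at a time. Sections 6.3 and 6.4 set reporting times for serious events but do not say how one participant's arm would be found. The locked codes at the sponsor's institute are the originals and are not offered as an emergency route.

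**4. Who might read the code.** The holder is one co-investigator. Section 8.3 lists a co-investigator physician in each of the two countries and one further co-investigator, so the holder may or may not be a site physician. This matters because section 6.1 has the study physician judge the intensity of adverse events, and the exclusion criteria include a doctor's judgement. In the section 4.6 schedule the examinations fall 1 to 3 days before treatment, ahead of randomisation at 0 h.

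**5. How much recruitment could remain.** Section 4.5 caps each trial at 2 months, with screening from four weeks before treatment and follow-up at 3 to 4 weeks. Taken literally, with 2 months as 60 days, the dosing window is 60 − 28 − 28 = 4 to 60 − 28 − 21 = 11 days. The cap may instead be per participant, and the synopsis dates span 08/2019 to 08/2021. The number still to be randomised at an opening therefore cannot be fixed; it could be few or none.

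**6. Whether 5.4 limits the exposure.** Dispensing from containers by a list creates no break for one participant. If the list were masked by a single label per drug, learning one participant's drug would decode the list for anyone holding it. The documents do not say how the list or containers are labelled, so this is a condition for the remedy to meet, not a defect shown.

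**The case against.** The best case for the plan is that harm needs a chain of unlikely steps: an emergency that calls for the code, occurring early enough to matter, with the contents reaching people who enrol or assess. Each link is weak. Treatment is a single dose, and the background and section 9.2 describe mainly mild events. Section 5.4 pauses the study after any serious adverse event until the data are reviewed and "a decision taken within the entire study team" follows, so randomisation would probably have stopped when the code was opened. Cure is read by microscopy, and nothing says technicians would be told. Section 7.3 analyses adverse events descriptively, section 4.6 uses a standardised symptom questionnaire, and section 6.2 allows a nurse to do the 24-hour interview. All of this stands and limits the weight of the point. None of it supplies a participant-level break.

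Some stronger readings are tempting but unsupported:

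- **Everyone consulted sees the code.** Section 4.4 says who decides on an emergency, not who reads the copy.
- **No independent person could take the unblinded look.** Section 11.2 sets up no monitoring board, but 4.4 has an uninvolved statistician and 11.2 keeps advisors informed.
- **The dispenser is unblinded from the start.** The labelling is not described, and the double-dummy masks participants and any staff who see neither container nor list.
- **An opening is likely, or would come with much of the sample still to be randomised.** The documents give no emergency rate, and the timing in 4.5 and the hold in 5.4 tell against the second part.

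A separate procedure could also exist, but the protocol mentions none.

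**Conclusion.** The point holds as a weakness of procedure. As worded, one opening discloses 350 of 350 trial B assignments, or one country's share, where 1 of 350 is needed, in tension with the double-blind design and the plan's own commitment on keeping the blind. This rests on the plain reading of 4.4: one envelope, one copy, the full code.

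The practical risk is probably small and depends on events that may never occur. The effect on cure or adverse event rates cannot be computed from the documents, and there is no ground for saying the primary comparison is biased. The change is worth making because it is a better method at very little cost.

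**What to change.** In section 4.4, replace the single sealed copy with individually sealed breaks, one per participant number, available in each country. Name who holds them, and log every opening with date, participant number, reason and who read it. Keep the full code only with the uninvolved statistician and in the locked cabinet.

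In section 5.4, state that the list and containers used for trial B dispensing are masked so that one participant's break does not decode the rest, and say who holds the list.

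The cost is about 350 sealed slips per country set (2 × 350 = 700 if both countries hold a full set), a log and a few sentences of text. No extra staff are needed, and dose, sample size and analysis stay as they are.

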## 4.5. Study duration and duration of subject participation

The trial will last a maximum of 2 months, each (trial A and B). The screening for the baseline will start four weeks prior to the treatment. Follow up screening will take place 3-4 weeks post-treatment. Schedules of visits are summarized below (Table 1).

## 4.6. Schedule of visits

Table 1. Schedule of visits of DF (trial A) and parallel group (trial B) study.

Screening /					Follow up		
Time point	Day -28	Day -1-3	0 h	л	3 h	24 h	Day 28
Informed consent	х			ando			
Diagnosis (stool examination) (a)	х			Randomization			х
Questionnaire	х			on and			
Medical history (c)		х					
Clinical examination (d)		Х		ninistr			
Physical examination (e)		х		administration of			
Randomization administration of treatment			х				
Capturing AEs (f)				treatment	х	Х	х
Capturing SAE (f)				1t	х	х	х

(a) on three stool samples duplicate Baermann assays and on two stool samples duplicate Kato-Katz thick smears. (b) date of birth, age, sex, height, weight, body temperature, pulse rate, blood pressure, hb measurement, pregnancy test and recording of breastfeeding

(c) information gained by asking specific questions concerning chronic disease and concomitant medication.

(d) investigation for signs of disease: head ache, abdominal pain, nausea, vomiting, diarrhea, itching, other symptoms. (e) examination on ear, nose, throat, eyes, lungs, lymph nodes and skin.

(f) a standardized symptom questionnaire is used, that includes the recording of headache, abdominal pain, itching, nausea, vomiting, diarrhea, allergic reaction, others

(g) only in trial B

# 5. Selection of the trial subjects

#### 5.1. Recruitment

The studies will be carried out in adults in areas endemic for *S. stercoralis* in Laos and Cambodia.

The adult community members will be invited to participate in an information meeting to explain the purpose and procedures of the study, including potential benefits and risks. Potential participants will be encouraged to ask questions in an open discussion forum.

Those adults who are interested in the study will be invited to complete the process of informed consent. See section 9.3 for details on obtaining informed consent. Only those participants who have written informed consent will be assessed for study eligibility criteria during screening procedures.

#### 5.2. Inclusion criteria

- Males and females of age 18 65 infected with *S. stercoralis (*positive by at least two Baermann assays of two different days and infection intensities of at least 0.1 LPG in the two stool samples (5g stool / Baermann assay).
- 2. Written informed consent signed by the participant him/herself. In case the person is illiterate, an impartial witness that can read and write has to sign the consent and the illiterate participant to give a thumb print.
- 3. Agree to comply with the study procedures, including to be examined by a study physician at the beginning of the study and to provide three stool samples at the beginning (baseline) and three stool samples approximately four weeks after treatment (follow-up).

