# 3. Trial objective and purpose

#### The primary study objectives are

- (A) To determine the nature of the dose-response (efficacy in terms of cure rate) using oral moxidectin dosages: 2 mg, 4 mg, 6 mg, 8 mg, 10 mg, 12 mg and placebo in a total of 210 adults infected with *S. stercoralis* (trial A: DF study).
- (B) To determine if the efficacy in terms of cure rate of an oral single optimal dose of moxidectin (8 mg based on the outcome of (A)) is non-inferior to the standard dose of a single oral ivermectin application (200 μg/kg), in 350 infected adults in two settings. The non-inferiority margin is set to 10%-points (trial B: parallel group study).

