#### 4.3.1. Baseline larval count

At baseline, all participants will be asked to provide three stool samples (if possible on three consecutive days or otherwise within a total maximum of 6 days) [23, 24]. The stool samples Page **18** of **45** 

will be collected until a total of 210 and 350 *S. stercoralis*-infected adults are registered (two out of three stool samples show more than 0.4 LPG (trial A) or 0.1 LPG (trial B), in 10 g of stool sampled per person and time point) in the two studies, respectively. As diagnosing very low-intensity chronic infections remains a major challenge for quantitative and qualitative analysis for *S. stercoralis* only low/moderate to high infection patients are included in trial A (LPG >0.4 on two out of three samples). This inclusion criterion has been shown to result in a diagnostic sensitivity of more than 97% to close to 100%. [24].

Firstly, a quantitative Baermann funnel concentration technique will be used for the quantitative assessment of *Strongyloides stercoralis* infections [24-26] using stool samples from three different (optimal consecutive) days. 5 g stool sample (the stool container with the sample will be weighted before and after the Baermann test was set up) will be placed on gauze inserted into a glass funnel and covered with preheated water to 36°C. Following two hours of artificial light exposure, the collected liquid will be centrifuged and the sediment prepared for analysis by microscope. Duplicate Baermann will be prepared from each stool sample [27, 28]. Secondly, from two stool samples from each participant a duplicate Kato-Katz thick smear will be prepared to detect co-infection with any of the three major soil-transmitted helminthic infections (STHs), namely *Ascaris lumbricoides, Trichuris trichiura* and the hookworms (*Necator americanus* and *Ancylostoma duodenale*) [29]. If additional coinfections are observed, they will be assessed likewise.

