#### 7.3. Description of statistical methods

An available case analysis (full analysis set according to the intention to treat principle) will be performed, including all subjects with primary end point data. Supplementary, a per-protocol analysis will be conducted. CRs will be calculated as the percentage of worm-positive adults at baseline who become worm-negative after treatment. LPG will be assessed by calculating the mean of the larvae counts from the three duplicate Baermann assays and relate this value to the mean weighted amount of stool sample. The LRR will be calculated (LRR = (1-(mean at follow-up/mean at baseline))\*100).

AEs will be evaluated descriptively as the difference of proportion reporting adverse events before and after treatment.

Trial A:  $E_{max}$  models using the Dose Finding package of the statistical software environment R will be implemented to predict the dose-response curves in terms of CRs and LRRs. Noncompartmental and nonlinear mixed-effects (NLME) modeling will be used to determine pharmacokinetic parameters.

On the basis of the LC-MS/MS measurements, the following PK parameters for plasma, whole blood and capillary blood will be calculated:

• Cmax maximal plasma concentration

- tmax time to reach Cmax
- AUC area under the curve, from 0 to 24h and 0 to inf.
- t1/2 elimination half-life

 $C_{max}$  and  $t_{max}$  will be observed values derived from the plasma concentration time profile. AUC and  $t_{1/2}$  will calculated with the software WinNonlin (Version 5.2, Pharsight Corporation, USA) using compartmental analysis. The elimination half-life will be estimated by the equation:  $t_{1/2} = ln2/\lambda$ , where  $\lambda$  will be determined by performing a regression of the natural logarithm of the concentration values during the elimination period.

Trial B: The non-inferiority margin is set to 10%-points, i.e. if the lower bound of the 95% CI of the differences in cure rates is greater than -0.1 we conclude that moxidectin is non-inferior to ivermectin. The 95% confidence interval of the differences in CRs will be estimated using the standard formula:

 $CI = (CR_{mox} - CR_{iver}) + - Z_{a/2} * \sqrt{(SE_{mox}^2 + SE_{iver}^2)}.$ 

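### Section 5.2 gives one intensity limit (0.1 larvae per gram) with no exception for trial A, against 0.4 in 4.3.1 and 4.4; for trial B the sections differ on whether exactly 0.1 qualifies

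*Combined protocol and SAP*

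**What the plan says.** Three sections of the combined protocol and SAP set or imply an entry threshold, and none is said to govern.

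- **Section 5.2, criterion 1:** larvae on two different days with "infection intensities of at least 0.1 LPG in the two stool samples (5g stool / Baermann assay". No trial is named. Section 5.1 speaks of the studies in the plural, so the list covers both.
- **Section 4.3.1:** participants are registered when "two out of three stool samples show more than 0.4 LPG (trial A) or 0.1 LPG (trial B), in 10 g of stool". The trial A rule is then repeated as "LPG >0.4 on two out of three samples", with the justification "This inclusion criterion has been shown to result in a diagnostic sensitivity of more than 97% to close to 100" per cent.
- **Section 4.4:** the light randomisation stratum starts, with a greater-than-or-equal sign, at "0.4 (trial A) or 0.1 (trial B") and runs to 1 LPG.

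Two details bear on how a limit is applied. Section 4.3.1 has the stool weighed: "the stool container with the sample will be weighted before and after the Baermann test was set up". Section 7.3 defines LPG across all three samples ("LPG will be assessed by calculating the mean of the larvae counts from the three duplicate Baermann assays and relate this value" to the mean stool weight), whereas 5.2 and 4.3.1 judge single samples. Section 4.4 does not say which quantity assigns the stratum.

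**The concern.** The threshold decides who is enrolled. Section 4.3.1 explains why trial A sets its limit higher: very light chronic infection is hard to diagnose, and the sensitivity claim is attached to the limit of 0.4. That claim does not cover anyone admitted to trial A at 0.1 to 0.4 LPG under 5.2. Cure in 4.3.4 means no larvae in any follow-up sample, so entry intensity bears on how securely a negative follow-up can be read as cure. An eligibility checklist would naturally be built from the section headed inclusion criteria, and for trial A that section has the wrong limit.

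For trial B the nominal limit is the same everywhere, but the sign is not. Trial B recruits in Laos and Cambodia, and the two teams could use different minimum counts while each follows a section of the protocol.

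**Working it through.** **No planned figure depends on the threshold.** The trial B sample size in 7.2 reproduces without it: n = (1.960 + 0.842)² × 2 × 0.89 × 0.11 / 0.10² = 7.85 × 0.1958 / 0.01 = 153.7, so 154 per arm, as stated.

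**Converting limits to counts.** Section 4.3.1 uses duplicate assays of 5 g, so 2 × 5 = 10 g per sample, and LPG = larvae / 10 at nominal weight. The table takes the same count in each sample and reads the sign in 4.3.1 and in 4.4 as applying to both trials' numbers.

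| Larvae per 10 g | LPG | A: 5.2 (≥0.1) | A: 4.3.1 (>0.4) | A: 4.4 (≥0.4) | B: 5.2 (≥0.1) | B: 4.3.1 (>0.1) | B: 4.4 (≥0.1) |
|---|---|---|---|---|---|---|---|
| 1 | 0.1 | in | out | no stratum | in | out | light |
| 2–3 | 0.2–0.3 | in | out | no stratum | in | in | light |
| 4 | 0.4 | in | out | light | in | in | light |
| 5 | 0.5 | in | in | light | in | in | light |

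In trial A the sections agree only from 5 larvae upward. In trial B they disagree only at 1 larva.

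**Effect of weighing.** 1/9.9 = 0.101 and 1/10.1 = 0.099; 4/9.9 = 0.404 and 4/10.1 = 0.396. At a limit, 0.1 g of stool decides entry. A larva-count rule placed beside a weighed LPG rule would therefore contradict it.

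**Strata, if the three-sample mean of 7.3 is used (an assumption).** Mean = total larvae / 30 g. Trial A patterns that meet 4.3.1 but fall below 0.4 are 5,5,0 (10/30 = 0.33), and 5,5,1 and 6,5,0 (11/30 = 0.37 each). In trial B, 1,1,0 gives 2/30 = 0.067 and has no stratum if entry is at least 0.1. If entry is more than 0.1, the lowest pattern is 2,2,0 (4/30 = 0.133) and none is lost.

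**Illustration of why entry intensity matters.** The model and the dispersion k are assumed. For an uncured person with mean m larvae per sample, the chance of three negative samples is exp(−3m) under Poisson, or (1 + m/k)^(−3k) under a negative binomial. At m = 1 this is 5.0% (Poisson) to 19.2% (k = 0.5). At m = 5 it is below 0.001% to 2.7%.

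**Does this move the trial A estimates?** Averaged over m = 1 to 4, the chance is 1.31% (Poisson) to 9.32% (k = 0.5). Let an assumed share s of 10–50% enter at 0.1–0.4 LPG. Apparent placebo cure is then 2.63–7.05% if added to the planned 2.5% (0.025 + 0.975 × s × mean), or 1.90–5.91% as a mixture ((1 − s) × 0.025 + s × mean). These ranges lie on both sides of 2.5%, and the shift is smaller than the 9-point precision in 7.2.

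**The case against.** The best defence is that the sections can be read together: 5.2 as a common floor and 4.3.1 as the trial-specific rule. Section 4.3.1 gives the trial A limit twice and calls it an inclusion criterion, and 4.4 has no trial A stratum below 0.4. The intent for trial A is therefore recoverable, and this part of the defence stands. It does not make 5.2 correct as written, because nothing there points to a stricter rule.

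Trial A also appears to be finished. Section 3 gives the trial B dose as "8 mg based on the outcome of (A"), the synopsis and 4.3 say much the same, and this version is dated 01.07.2020 against a planned first participant in 08/2019. The synopsis still says the dose depends on trial A, so completion is likely but not certain. This moves the trial A remedy from enrolment to reporting.

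On trial B, it can be said that with weighed stool almost nobody sits exactly at 0.1 LPG. That is fair. The sign decides entry only where LPG is worked out on the nominal 10 g or rounded to one decimal, and the protocol does not say how it is computed for eligibility.

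Some stronger readings are tempting and do not hold:

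- **Sites applying 0.1 and 0.4 side by side.** Trial A is planned in one setting in northern Laos, so this gap cannot split countries.
- **Conflicting stool weights, 5 g against 10 g.** Duplicate assays of 5 g are 10 g.
- **A certain gap in the strata.** It arises only if 4.4 uses the three-sample mean, and the few patterns affected would naturally be classed as light.

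**Conclusion.** The contradiction is real and in current text. For trial A, 5.2 admits people with 1 to 4 larvae per nominal 10 g whom 4.3.1 excludes, and 4.4 has no stratum for 1 to 3. For trial B, the sections differ at 1 larva per nominal 10 g.

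Severity is minor. A reader might infer biased comparisons or inflated cure rates, but the documents do not support either. Eligibility is settled before randomisation, so the arms stay comparable; the sample size is untouched; and neither the size nor the direction of any effect on cure rates can be fixed without assumed shares and dispersion. The documents also do not show that anyone was enrolled under the wrong limit.

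The conclusion rests on two readings: that 5.2 covers both trials, and that the sign in 4.3.1 applies to both numbers.

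**What to change.** 1. In 5.2 criterion 1, state the limit per trial, met in at least two of three baseline samples: more than 0.4 LPG for trial A and at least 0.1 LPG for trial B. Define LPG per sample as larvae in both duplicate assays divided by weighed stool, and state any rounding. Add no separate larva-count test.
2. Use the same signs in 4.3.1 and 4.4. For trial B, at least 0.1 needs the fewest edits because 5.2 already says it.
3. In 4.4, name the LPG quantity that assigns the stratum, and define light as any eligible participant up to and including 1 LPG.
4. If trial A enrolment is closed, report which limit was applied and how many participants entered at or below 0.4 LPG. If there are any, refit the Emax model without them as a sensitivity analysis.

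The cost is amended wording in three sections, with the ethics approval that 8.1 requires, and one revised eligibility checklist. If trial A is closed, add one count and at most one refit on data already collected. No visit, sample or procedure is added.
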